### 8.2 Primary Measured Outcomes

- Safety

The measured safety outcome is the proportion of subjects with neurological death or ipsilateral stroke within the first 30 days following completion the first PHIL of treatment procedure. The descriptive analysis of this outcome will include the number of subjects with neurological death or ipsilateral stroke, the total number evaluated, the percent, and the Clopper-Pearson two-sided 95% confidence limits on the percent.

- Probable benefit

The measured probable benefit outcome is the angiographic occlusion of the pre-specified target vessel intended for treatment at procedure following completion of the first PHIL treatment procedure. The descriptive analysis of this outcome will include the number of subjects with angiographic occlusion of treated vessel at procedure, the total number evaluated, the percent, and the Clopper-Pearson two-sided 95% confidence limits on the percent.

### **8.3 Secondary Measured Outcomes**

The descriptive analysis of the following secondary measured outcomes will include the number of subjects with the outcomes of interest, the total number evaluated, the percent, and the Clopper-Pearson two-sided 95% confidence limits on the percent.

- The proportion of subjects with neurological death or ipsilateral stroke within the first 30 days following completion of all PHIL treatments
- Angiographic occlusion of the pre-specified target vessel intended for treatment at procedure following completion of all PHIL treatments
- New-onset or worsening of permanent morbidity at 6 month follow-up
- New-onset intracranial hemorrhage at 6 month follow-up
- New-onset of cranial nerve palsy at 6 month follow-up
- Clinically significant technical events during the PHIL embolization procedure(s) including but not limited to reflux of embolic material, migration of the embolic material, catheter entrapment or damage, and vessel dissection.
- Device-related adverse events at procedure and 30 days
- Device-related mortality at procedure and 30 days
- Procedure related adverse events including complications of arterial puncture, contrast-induced nephropathy, radiation-induced injuries, renal and anesthesia-related complications.

- New-onset of device/procedure-related neurological adverse event or worsening of previous neurological deficit unresolved at 6 month follow-up.

#### **8.4 Additional Measured Outcomes**

The descriptive analysis of the following additional measured outcomes will include the number of subjects with the outcomes of interest, the total number evaluated, the percent, and the Clopper-Pearson 95% confidence limits on the percent.

- Improvement of neurological symptoms
- Unplanned adjunctive treatments

The descriptive analysis of the following additional measured outcomes will include N, mean, median, standard deviation, minimum and maximum value.

- Procedure time (defined as first to last fluoroscopic or digital subtraction angiographic acquisitions)
- Radiation exposure (dosage and time)
- Injected volume of PHIL

The descriptive analysis of the following additional measured outcomes will include the number of subjects at each category and the percentage of each category.

- Number of procedures required to treat the fistula at 6 months follow-up
- Modified Rankin Scale (mRS) at 3 and 6 months
- Self-reported QOL questionnaire, EQ-5D at 6 months

#### **8.5 Duration Variables**

Study Day 1 is the day of study device deployment (index procedure). Study day will appear in the listings where applicable and is calculated relative to day 1 using the general formula:

Study Day = (Date of Event – Date of Study Device Deployment) +1, if event date is on or after Date of Study Device Deployment

Study Day = (Date of Event – Date of Study Device Deployment), if event date is before the Date of Study Device Deployment

Duration variables will be calculated using the general formula:

$$[(\text{end date} - \text{start date})] + 1$$

## 8.6 Handling of Missing Data

If there is missing data in primary and secondary outcome, sensitivity analysis will be performed on the imputed data.

Subjects whose data are not missing at random, such as those who exit the study due to a device-related primary safety event, will be considered a failure for the probable benefit endpoint and will be considered to have a primary safety event for the primary safety endpoint.

Subjects with missing data who exit the study due to a non-device-related primary safety event will be imputed by the multiple imputation methods; similarly, their missing probable benefit endpoint will also be imputed by the multiple imputation methods.

Subjects who are absent at post-procedure visits and can be assumed to be missing at random, will have their success or failure imputed for the primary safety and probable benefit endpoints. For example, if a study stops follow-up for reasons other than a device-related primary safety event, that subject will be imputed by the methods discussed below.

For multiple imputation methods, the assumption is that data from subjects undergoing imputation is missing at random (Little and Rubin (2000)). A comprehensive sensitivity analyses called the tipping point analysis will be done. In this analysis, one can start with either the worst-case analysis in which all missing at random data will be assigned a failure for the primary endpoint, or can be started with the best case scenario in which all missing at random subjects will be assigned a success for the primary endpoint. The tipping point analysis provides result for all possible outcomes from the imputation process and is thus comprehensive.

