4.4.1 SUBJECT WITHDRAWAL

All enrolled subjects have the right to withdraw their consent at any time during this study. All data collected until the time of subject withdrawal will remain in the study database and will be used for analysis. Whenever possible, the site staff should obtain written documentation from the subject who wishes to withdraw his/her consent for future follow-up visits. If the site staff is unable to obtain written documentation, all information regarding the subject's withdrawal must be recorded in the subject's medical record. In addition, the appropriate eCRFs must be completed for the subject and clear documentation of the subject's withdrawal should be provided to the Sponsor.

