#### **4.1 Primary Measured Outcomes**

The following outcomes will be measured:

- Safety: The proportion of subjects with neurological death or ipsilateral stroke within the first 30 days following completion of the first PHIL treatment procedure.
- Probable benefit: Angiographic occlusion of the pre-specified target vessel intended for treatment at procedure following completion of the first PHIL treatment procedure.

Neurologic death is subject death reported as having resulted from a neurologic cause. Stroke is defined as a new focal neurological deficit in a defined vascular distribution of abrupt onset with symptoms persisting for >24 hours AND a neuro-imaging study or other quantitative study that does not indicate a different etiology. This includes ischemic and hemorrhagic strokes.

Angiographic occlusion of the pre-specified target vessel is defined as cessation of flow at the point of embolic agent administration at the target vessel.

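### SAP 8.6 sends subjects who exit because of a non-device-related primary safety event to imputation, so the sensitivity analysis can score known events as non-events

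*SAP*

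**What the plan says.** SAP 4.1 defines the primary safety outcome as "The proportion of subjects with neurological death or ipsilateral stroke within the first 30 days following completion of the first PHIL treatment procedure". Neither that section nor its definitions of neurologic death and stroke mention relatedness to device or procedure. SAP 8.2 reports "the number of subjects with neurological death or ipsilateral stroke, the total number evaluated, the percent" with Clopper-Pearson limits, again without a relatedness filter.

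SAP 8.6 opens with "If there is missing data in primary and secondary outcome, sensitivity analysis will be performed on the imputed data". It then sets out three groups:

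- **Exit because of a device-related primary safety event.** Treated as not missing at random and scored as having the safety event.
- **Exit because of a non-device-related primary safety event.** "Subjects with missing data who exit the study due to a non-device-related primary safety event will be imputed by the multiple imputation methods", and the same sentence extends this to their missing probable benefit result.
- **Absent from post-procedure visits and assumed missing at random.** Imputed for both primary endpoints. The example given is that "if a study stops follow-up for reasons other than a device-related primary safety event, that subject will be imputed".

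Multiple imputation is stated to rest on missing at random. A tipping-point analysis follows, one end of which is the "best case scenario in which all missing at random subjects will be assigned a success for the primary endpoint".

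Protocol 4.4.1, on subject withdrawal, states: "All data collected until the time of subject withdrawal will remain in the study database and will be used for analysis".

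**The concern.** A subject who leaves because of a primary safety event has, by definition, had the primary safety outcome. Device-relatedness is not part of that outcome, so it cannot decide whether the outcome is known. SAP 8.6 uses it that way: one relatedness call keeps the event, and any other call hands the subject to a model that may return a non-event.

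The missing-at-random assumption also fails for this group, because the outcome itself caused the exit. That is the same reasoning by which the SAP treats the device-related exits as not missing at random.

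A missing-data sensitivity analysis should show how far unknown outcomes could move the safety rate. Here it could also move the rate downward on outcomes that are known. A reader who saw a sensitivity rate below the SAP 8.2 rate would take it as information about missing data, when it reflected an attribution call outside the outcome definition. In a single-arm study whose rates may be compared with the literature (SAP 8.1), that would be a misleading supplementary safety estimate.

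**Working it through.** **Can the group exist?** Protocol 7.2.1 lists five relatedness categories: study disease, concomitant disease, procedure, device and unknown. Events attributable to other devices used at the procedure, such as delivery microcatheters or guidewires, fall under procedure-related. A stroke caused by the delivery microcatheter would therefore be a primary safety event without being device-related, as would a neurological death attributed to the fistula itself. A death also necessarily ends participation.

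**Does the imputation rule reach the safety endpoint?** Three features of SAP 8.6 say so:

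1. The paragraph just before scores the safety endpoint explicitly for the device-related counterpart.
2. The sentence adds probable benefit as a further item imputed in the same way, so its first clause most naturally concerns safety.
3. The next paragraph names the primary safety endpoint, and its example covers every reason for stopping except a device-related primary safety event.

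In addition, Protocol 6 has first-procedure occlusion measured intra-operatively, so a later exit would seldom leave the primary benefit outcome missing.

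**The plan's own figure.** The only design number is enrolment: 60 subjects with 6-month follow-up plus 15 lost gives 75, equivalently 60/(1 − 15/75) = 75. It reproduces and is not in dispute.

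**Inputs for the illustration.**

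- n = 75, from SAP 6.
- T, the number of recorded primary safety events: assumed.
- k, the number of those who exit with a non-device-related event: assumed.
- No other missing subjects, and imputation at the remaining subjects' rate without covariates: assumed, because the SAP names no imputation model.

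**Formulas.**

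- Recorded rate = T/75
- Rate among remaining subjects: r = (T − k)/(75 − k)
- Mean imputed rate = (T − k + k·r)/75, which simplifies to r
- Tipping-point best case = (T − k)/75; worst case = T/75

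**Results.**

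| T | k | Recorded | r | Mean imputed rate |
|---|---|---|---|---|
| 6 | 0 | 8.0% | 6/75 | 8.0% |
| 6 | 1 | 8.0% | 5/74 | 6.8% |
| 6 | 2 | 8.0% | 4/73 | 5.5% |
| 6 | 3 | 8.0% | 3/72 | 4.2% |
| 3 | 2 | 4.0% | 1/73 | 1.4% |
| 9 | 2 | 12.0% | 7/73 | 9.6% |
| 11 | 2 | 14.7% | 9/73 | 12.3% |

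The last row takes T = 11 because 11/75 lies just under the roughly 15% that Protocol 3.1 expects as a ceiling.

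**Tipping point with T = 6 and k = 2** (Clopper-Pearson 95% limits):

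- Best case: 4/75 = 5.3% (1.5 to 13.1)
- Worst case: 6/75 = 8.0% (3.0 to 16.6)

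Only the worst-case end equals the recorded result, although no outcome in this example is unknown.

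**The case against.** The strongest counter-argument is that the rule covers only missing data. The section is about missing data, the sentence begins with subjects who have some, and multiple imputation fills gaps rather than overwriting observed values. Nothing in SAP 8.6 tells anyone to delete a recorded event. The rule also has legitimate targets: a subject who leaves after an early stroke lacks the 6-month secondary outcomes in SAP 4.2, which the opening sentence of 8.6 covers. Read with Protocol 4.4.1, a recorded event would stay an event.

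This reading is possible, and imputing those secondary outcomes is reasonable. It does not explain why the text separates device-related from non-device-related primary safety events, scores safety explicitly for the former and imputes the latter. If every recorded event were kept anyway, that split would serve no purpose for the safety endpoint. If the sponsor does intend the narrow reading, the proposed wording simply states it.

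Other points stand as limits:

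- The SAP 8.2 count has no imputation and would include these events.
- Outcomes are adjudicated by an independent committee (Protocol 7.4), and all recorded data are listed.
- Protocol 4.4.1 concerns withdrawal of consent, so it supports the principle rather than settling every kind of exit.
- Protocol 7.1 has adverse events followed to resolution or the end of 6-month follow-up, so a stroke need not lead to exit, and such exits may be few or none.
- The event and exit counts are assumed. The illustrated means for T = 6 lie within the recorded interval of 3.0% to 16.6%.

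**Conclusion.** The concern holds. SAP 8.6 makes the handling of a known primary safety event depend on device-relatedness, which the outcome definition does not contain. Under the simple model above, any such exit lowers the expected sensitivity rate below the recorded rate. With 6 events in 75, the fall is about 1.2, 2.5 or 3.8 percentage points for one, two or three exits (8.0 − 6.8, 8.0 − 5.5, 8.0 − 4.2). A different imputation model would give different figures, and with no such exits there is no effect.

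The reach is limited to the sensitivity analysis. The SAP 8.2 result is not shown to change, and the study is descriptive with no success criterion, so no formal decision turns on it. It should be fixed because the error is avoidable and bears on the primary safety outcome.

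**What to change.** Revise SAP 8.6 to state:

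> Any subject with a recorded neurological death or ipsilateral stroke within 30 days of the first PHIL procedure is counted as having the primary safety event in the main and all sensitivity analyses, regardless of relatedness or study exit. Imputation and tipping-point assignment for this endpoint apply only to subjects whose 30-day status is unknown.

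The existing sentence on non-device-related exits should then be confined to outcomes that really are missing for those subjects, such as the 6-month secondary outcomes.

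The cost is a two-sentence addition and that consequential edit. It needs no new data and leaves the SAP 8.2 analysis unchanged. If such exits occur, the sensitivity estimate may look less favourable.

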## 8.7 Software

All statistical analyses will be performed using Statistical Analysis System (SAS) for Windows (version 9.4, SAS Institute Inc. Cary, NC) .

## 9. Changes in Planned Analyses

Any deviations or changes from this SAP deemed necessary due to violation of critical underlying statistical assumptions, data characteristics, or missing data will be clearly described with justification and rationale.
